### **3 STUDY DESIGN**

#### Type/Design of Trial:

We will conduct a pragmatic cluster-randomized clinical trial of this simple non-pharmacologic intervention by training a cohort of Clinician Value Champions in primary care clinic settings across two large accountable care organizations (ACOs); Oschner Health, and United States Medical Management (USMM).

#### Primary & Secondary Outcomes by Specific Aim:

Specific Aim #1: The primary outcome for this study will be medication possession rates (MPR) per quarter, for the 3 therapeutic classes of PIMs - antipsychotics, benzodiazepines, and hypoglycemics using currently available Medicare claims data from each participating ACO. These beneficiary-level measures are calculated as quotients with denominator equal to the length of the quarter and the numerators equal to the days supply for prescriptions within the class filled during the quarter, plus excess days-supply from the previous period minus excess days-supply remaining at the end. Unlike many studies using medication possession rates to exam adherence, we are interested in reducing, not increasing, the percent of days covered.

Specific Aim #2: As a secondary outcome, we will also assess the incidence of falls during the study window. Falls are difficult to monitor using claims data, but Min and colleagues have developed a method that IAC and Brandeis staff (Co-Investigator [name]) have helped test for ICD-10. We will use the most conservative definition that looks for the presence of fall 'reason for visit' code on ED, ambulatory, or inpatient visit as indicated by a clinician bill (Part B).

Specific Aim #3: The five important implementation outcomes: appropriateness, fidelity, feasibility, and penetration will be assessed by analysis of interviews conducted with a group (approximately 8) of clinician value champions who have completed the webinar training.

#### Study Population:

Clinician practices within each ACO will be eligible for participation in the study if they include 3 or more primary care providers (defined as a primary care physician (specialty code of 08 or 11), nurse practitioner (specialty code = 50) or physician's assistant (specialty code = 97)) and treat 10 or more Medicare beneficiaries with Alzheimer's or Alzheimer's related dementia in the base years (2019-2020). Medicare beneficiaries within the claims data provided by the two ACOs will be included in the study if they meet all of the following criteria during the intervention year: a. they are seen by a clinician at a participating practice as evidenced by one or more evaluation and management claim, b. they have continuous coverage in Medicare Parts A, B and D and no months of Part C (Medicare Advantage), they have two or more claims with an ICD-10 diagnosis for Alzheimer's or Alzheimer's related dementia 30 days apart or 1 inpatient stay with a principal diagnosis of Alzheimer's. Specific ICD-10 diagnoses to identify beneficiaries with Alzheimer's or Alzheimer's related dementia will be derived from a forthcoming paper by [name] and colleagues from the Technical Data Core of the Impact Collaboratory (personal communication, April 4, 2021). This definition is more inclusive than the CMS Chronic Condition Data Warehouse (CCW) definition of Alzheimer's and was

specifically designed for ICD-10. Patients with a diagnosis of metastatic cancer or enrolled in hospice any time in the 6 months before the start of the intervention will be excluded.

Randomization:

The unit of randomization will be the primary care practice. We anticipate 32 out of 39 teams from USMM to meet eligibility and 26 out of 28 practices for Ochsner. Within each ACO, we will randomly select half of the practices for participation in the value champion training and the remaining practices will continue with care as usual. Prior to random assignment, we will stratify all clinics/practices based on high versus low historic prescribing rates, with the cut-point for inclusion in the study based on the distribution of overall rates for all 3 therapeutic classes using data for 2019-2020. Once randomized, a clinician value champion will be recruited from each of the clinics randomized to the intervention arm of the study in partnership with the ACO leadership.

Study Locations: Primary care clinics within each of the two participating ACOs.

Duration of Enrollment and Follow-up: Using Medicare claims data for our primary outcome, with a follow-up period of one year after completion of the 6-months of value champion training, and with medication possession rates calculated per patient each quarter, we will have approximately 4 MPR observations per patient or 8,000 observations per group for USMM analyses and 2,000 per group for Ochsner.

## **4 SELECTION AND ENROLLMENT OF PARTICIPANTS**

### **4.1 Inclusion Criteria**

Clinician practices within two ACOs will be eligible for participation in the study if they meet the following criteria:

- a. They include 3 or more primary care providers (defined as a primary care physician (specialty code of 08 or 11), nurse practitioner (specialty code = 50) or physician's assistant (specialty code = 97)) and
- b. They have clinical encounters with 10 or more Medicare beneficiaries with Alzheimer's or Alzheimer's related dementia in the base years (2019-2020).

Medicare beneficiaries will be included in the study if they meet all of the following criteria during the intervention year:

- a. They are seen by a clinician at a participating practice as evidenced by one or more evaluation and management claim,
- b. They have continuous coverage in Medicare Parts A, B and D and no months of Part C (Medicare Advantage),
- c. They have two or more claims with an ICD-10 diagnosis for Alzheimer's or Alzheimer's related dementia 30 days apart or 1 inpatient stay with a principal diagnosis of Alzheimer's.

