### Design and Outcomes

This study is a pragmatic cluster-randomized trial to test the effectiveness of a primary care clinician value champion for de-implementing potentially inappropriate medications among patients 65 years of age and older with a diagnosis of dementia. Medicare Part D pharmacy claims data will be analyzed at the end of the 12-month intervention for the primary outcome, the medication possession rates (MPR) for three groups of potentially inappropriate medications: antipsychotic medications, benzodiazepines, and hypoglycemic medications (sulfonylureas and insulin). In a similar fashion, a hospital admission, or an emergency department visit for a fall will be assessed at the end of the intervention using Medicare claims data. Finally, the five implementation outcomes – Appropriateness, Fidelity, Feasibility, Penetration and Equity - will be evaluated through analysis of interviews conducted with participating clinician value champions.

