### Sample Size and Population

Medicare beneficiaries from claims data provided by each ACO will be included in the final outcome analysis if they meet all of the following criteria prior to the start of the intervention: a) they are seen by a clinician at a participating clinic as evidenced by one or more evaluation and management claims, b) they have continuous coverage in Medicare Parts A, B and D and no months of Part C (Medicare Advantage), and c) they have two or more claims with an ICD-10 diagnosis for Alzheimer's or Alzheimer's related dementia 30 days apart or 1 inpatient stay with a principal diagnosis of Alzheimer's. We anticipate a total of approximately 5,000 patients will be included in this final analysis across both ACOs.

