## 6.2 Description of Evaluations

### 6.2.1 Screening Evaluation

Screening for eligibility will be done by review of existing Medicare claims data from each ACO as described in Section 4.1 above.

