#### Screening

##### Patient Subjects:

Screening of eligible participants will be done by the programmer/analyst at IAC by applying study inclusion / exclusion criteria as described above in Section 4.1. This screening and selection will take place months 1-3 of the study prior to the value champion intervention. All Medicare beneficiaries at eligible ACOs will be included if they

meet eligibility criteria during the intervention year.

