## **9 STATISTICAL CONSIDERATIONS**

### **9.1 General Design Issues**

Our hypothesis is that for each medication class, the intervention will produce clinically relevant decreases in mean possession rates of 10% of a standard deviation in patients seen in intervention clinics compared to those who are seen in control group clinics.

The study design was chosen to meet the requirements of the funder for a non-pharmacologic/non-device intervention for people living with dementia, conducted in a health system setting. The 24-months of funding is for a demonstration project, intended to demonstrate the feasibility and acceptability of the intervention, but with the stipulation by the funder that the trial must be a randomized controlled trial, one with a control group. In response, we proposed a cluster-randomized trial where the intervention will be randomized at the primary care clinic level, not the patient level, and existing health systems claims data will be used to address our primary outcome (Specific Aim #1) and one of our secondary outcomes: Specific Aim #2: emergency department visits and hospitalizations for a fall.

The primary outcome measure for this study will be medication possession rates (MPR) per quarter, for the 3 therapeutic classes of medications - antipsychotics, benzodiazepines, and hypoglycemics - that are considered low-value for beneficiaries with dementia. Unlike many studies using medication possession rates to exam adherence, we are interested in reducing, not increasing, the percent of days covered. Following an intent-to-treat design, claims data from all Medicare beneficiaries meeting our dementia eligibility criteria prior to the start of the value champion intervention will be included in the analysis. To determine the impact of the intervention, we will construct hierarchical models with time period observations nested within patient. These models will be random effects or generalized estimating equations (GEE) with robust standard errors, and will be either linear, if original MPRs are used as outcome, or generalized linear, if transformation necessary. The key variable of interest in these models will be the treatment indicator (assigned based on practice randomization to intervention or control group).

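### The analysis cohort is fixed before the intervention in some sections and during the intervention year in others; the Section 4.1 rule selects patients on post-randomisation claims

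*Combined protocol and SAP*

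**What the plan says.** Two sections place eligibility before the intervention. In the Précis (Sample Size and Population), beneficiaries "will be included in the final outcome analysis if they meet all of the following criteria prior to the start of the intervention"; the criteria listed there are a visit claim, coverage and dementia diagnosis. Section 9.1, describing the intent-to-treat analysis, says that "claims data from all Medicare beneficiaries meeting our dementia eligibility criteria prior to the start of the value champion intervention will be included". It names only the dementia criteria.

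Two sections place the same visit, coverage and diagnosis criteria in the intervention year. Section 3 (Study Population) says beneficiaries "will be included in the study if they meet all of the following criteria during the intervention year", and Section 4.1 repeats it: "Medicare beneficiaries will be included in the study if they meet all of the following criteria during the intervention year".

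Section 6.2.1 (Screening, Patient Subjects) says both. "This screening and selection will take place months 1-3 of the study prior to the value champion intervention", yet beneficiaries are included if they "meet eligibility criteria during the intervention year". The opening of Section 6.2.1 sends the reader back to Section 4.1: "Screening for eligibility will be done by review of existing Medicare claims data from each ACO as described in Section 4.1 above".

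Section 9.5 repeats the intent-to-treat principle, whatever the patient's level of engagement with the clinicians, but gives no time window. The hospice exclusion in Section 4.2 looks back from the start of the intervention.

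**The concern.** Two analysts working from different sections would build different cohorts for the primary analysis. A patient diagnosed during the project year is in under Section 4.1 and out under the Précis. A patient who qualified beforehand but has no visit claim in the project year is in under the Précis and out under Section 4.1.

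The choice also affects validity. A cohort fixed on pre-randomisation claims cannot be altered by the assigned arm. A cohort defined by visits, dementia codes and coverage during the intervention year can be, if any of these come to differ between intervention and control clinics. The comparison would then mix a change in prescribing with a change in who is counted. With a target effect of only 0.10 SD per drug class, a modest imbalance in inclusion would matter.

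**Working it through.** **Timeline.**

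- Section 3 (Randomization): a champion is recruited only after the clinic has been randomised.
- Section 4.3: champions are recruited in months 1-3. Randomisation is therefore no later than that.
- Section 2 (description of the intervention): training runs in months 4-9 and the project phase starts at month 10.
- Section 3 (Duration of Enrollment and Follow-up): quarterly MPRs are taken over the year after training.

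The term intervention year is not formally defined, but on any reading it follows randomisation. If it is the project year, the Section 4.1 claims arise at least six months (months 4-9) after randomisation and in the same year as the outcome. Nor can screening of existing claims in months 1-3 use claims from a year that begins at month 10.

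**The start of the intervention is undated.** Section 2 counts training as a phase of the intervention, which gives month 4. The Précis (Design and Outcomes) says the claims "will be analyzed at the end of the 12-month intervention for the primary outcome", which gives month 10. Both fall after randomisation, so dating the start does not by itself keep post-randomisation claims out of the eligibility window.

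**The plan's own figures (Section 9.2).** Effective observations per group are 500 × 4 × 0.8 = 1,600 for Ochsner and 2,000 × 4 × 0.8 = 6,400 for USMM. Power, two-sided 5%, normal approximation, is Φ(d√(n/2) − 1.96):

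- n = 1,600, d = 0.10: 80.7% (stated 80%)
- n = 6,400, d = 0.10: 99.99% (stated almost 100%)
- n = 6,400, d = 0.05: 80.7% (stated 80%)

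The arithmetic reproduces. The patient counts behind it come from 2019 dementia rates and carry no eligibility window, so no corrected sample size can be derived.

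**Scale of a possible bias (assumed inputs).** Let p be the prevalence of use, s the excess share of added patients in the intervention arm beyond comparable additions in control, and r their use rate relative to the cohort. If MPR is either 0 or 1,

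shift in SD = s × (1 − r) × p/√(p(1 − p)), positive towards the intervention.

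Section 2.1 gives p = 0.143 for antipsychotics and, as the highest reported value, p = 0.20 for benzodiazepines. The factors p/√(p(1 − p)) are 0.4085 and 0.500. With s = 0.10:

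| Use rate of added patients (r) | Antipsychotics | Benzodiazepines |
|---|---|---|
| 0 (non-users) | +0.041 | +0.050 |
| 0.5 | +0.020 | +0.025 |
| 1 | 0 | 0 |
| 1.5 | −0.020 | −0.025 |
| 2 | −0.041 | −0.050 |

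With s = 0.05 each figure halves. For given p, s and r, all-or-none MPR is an upper bound on the size, because any spread in users' MPR lowers the ratio of mean to SD. If users' MPR is uniform on 0 to 1 (an assumption), the non-user shifts are 0.035 and 0.042 SD. Hypoglycemics are left out because Section 2.1 gives use only among patients with A1c below 7%.

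**The case against.** The best defence is that differential selection is hypothetical. A programmer applies the criteria to claims, not clinic staff. The intervention described in Section 5.1 targets prescribing, and nothing in the protocol says it will change visits, coding or coverage. This stands, and it limits what can be said about bias. It does not remove the conflict between the definitions.

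Nor is intent beyond dispute. Three sections, including the inclusion criteria themselves, use the intervention year, and patients seen during a clinic-wide initiative are a possible pragmatic target population. Only the Précis clearly places visits and coverage beforehand. This also stands: the documents demand reconciliation, while closing the window at or before randomisation is a design recommendation that no section states. In its favour, the two passages that speak of who enters the analysis both look backwards, as does the hospice exclusion.

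A reader might also see a third cohort rule in Section 10.1, which calls the patients an inception cohort. That may be loose usage for a cohort fixed at study start. Together with the planned description of incident versus prevalent dementia in Section 9.5, it does not establish another rule.

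**Conclusion.** The concern holds. The primary-analysis population has incompatible definitions, and Section 6.2.1 contradicts itself. The Section 4.1 version conditions on claims made after randomisation and during outcome measurement, at odds with the intent-to-treat set in Section 9.1. This must be settled before the cohort is drawn, and the reason is the conflict itself rather than a demonstrated bias.

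Three stronger readings are not supported:

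- A reader might infer that Section 4.1 will bias the result, or favour the intervention. The documents do not show selection differing by arm; size and direction are unknown, and the bias is nil if it does not differ. The 0.04-0.05 SD figure rests on an assumed 10% between-arm excess of non-users and all-or-none MPR, and shows scale only.
- A reader might infer that dating the start of the intervention is enough. It is not, since months 4 and 10 both follow randomisation.
- A reader might infer that the 80% power figures are wrong. Any new figure would need assumed loss and dilution, for which the documents give no baseline.

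**What to change.** Use one pre-intervention cohort in the Précis and in Sections 3, 4.1, 6.2.1, 9.1 and 9.5. Close the eligibility claims window on a stated calendar date at or before randomisation, identical in both arms, and apply the visit, coverage and diagnosis criteria within it. Do not make inclusion depend on visits, diagnoses or coverage after that date. Keep the intervention-year cohort as a labelled sensitivity analysis.

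The direct cost is aligned wording and a date in the claims query. There may be some loss of precision: newly diagnosed patients leave the primary analysis, and patients not seen again stay in and may dilute the effect. Not all such dilution comes from the change, because under Section 4.1 a patient first seen in the last quarter may also contribute quarters before any contact. Recheck the Section 9.2 counts and power once the cohort is fixed.

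Attribution of patients seen at more than one practice, and the handling of partly covered quarters, should be raised as separate points.

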#### 9.2.1 Treatment Assignment Procedures

The unit of randomization will be the primary care practice or team. We anticipate 32 out of 39 teams from USMM to meet eligibility and 26 out of 28 practices for Ochsner. Within each ACO, we will randomly select half of the practices for participation in the value champion training and the remaining practices will continue with care as usual. Prior to random assignment, we will stratify practices based on high versus low historic prescribing rates. We will select practices for randomization and inclusion using a cut-point based on the distribution of overall rates for all 3 therapeutic classes using data for 2019-2020. Once randomized, a clinician value champion will be recruited from each of the clinics randomized to the intervention arm of the study in partnership with the ACO leadership.

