### 9.5 Data Analyses

Following an intent-to-treat design, all Medicare beneficiaries meeting our dementia eligibility criteria will be included in the study, regardless of level of engagement with practice clinicians. Data analysis will begin with descriptive statistics, comparing the mix of patients at each practice including demographics, chronic conditions, and incident versus prevalent dementia. This will allow us to check for balance between treatment and control practices and inform subsequent modeling. To determine the impact of the intervention, we will construct hierarchical models with time period observations nested within patient. These models will be random effects or generalized estimating equations (GEE) with robust standard errors, and will be either linear, if original MPRs are used as outcome, or generalized linear, if transformation necessary. The key variable of interest in these models will be the treatment indicator (assigned based on practice). Since there could well be a time effect of treatment, we will explore several model specifications, such as discrete indicators for the time periods or a single continuous variable. Interactions of treatment with time period will also be explored. By examining various different specifications involving time, we should be able to determine whether the intervention leads to a one-time change, a gradual trend over time, or a combination of both (an immediate jump with a further change, as time passes). Finally, we will explore the impact of this intervention on health inequities by stratifying our primary analysis by race/ethnicity.

Specific to Aim #3: Current approaches to evaluating implementation outcomes are still nascent, with few measures that have validated psychometric properties. Conceptually, these measures are inter-dependent, and are connected with service outcomes, such as patient safety. We will use data collected from interviews with the Value Champions to conduct a thematic analysis of the five implementation outcomes using a deductive approach.

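### Patient cohort and arm can be set by visits after randomisation, and no rule says which practice counts for a patient seen at several

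*Combined protocol and SAP*

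**What the plan says.** **Entry.** Section 4.1 requires: "They are seen by a clinician at a participating practice as evidenced by one or more evaluation and management claim". The précis (Sample Size and Population) uses the same test: "they are seen by a clinician at a participating clinic as evidenced by one or more evaluation and management claims". Section 9.5 includes eligible beneficiaries "regardless of level of engagement with practice clinicians", so one visit is enough.

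**Window.** Section 4.1 reads: "Medicare beneficiaries will be included in the study if they meet all of the following criteria during the intervention year". Section 3 (Study Population) agrees. The précis instead counts beneficiaries "if they meet all of the following criteria prior to the start of the intervention". Section 9.1 also dates the dementia eligibility criteria before the intervention. The screening text in section 6.2.1 contains both: it schedules patient screening in months 1-3, before the intervention, and then applies criteria met during the intervention year.

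**Arm.** Section 9.2.1: "The unit of randomization will be the primary care practice or team". Half of the practices in each ACO go to each arm. Section 9.1: "The key variable of interest in these models will be the treatment indicator (assigned based on practice randomization to intervention or control group". Section 9.5 repeats that the indicator follows the practice.

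**Not stated.** There is no rule for a patient with claims at more than one participating practice. Section 4.2 excludes only metastatic cancer and hospice enrolment. No sensitivity analysis deals with patients seen in both arms.

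**The concern.** Sections 9.1 and 9.5 describe the analysis as intent-to-treat. In a practice-randomised trial, that requires the cohort and each patient's arm to be fixed by facts that the intervention cannot influence. A visit during the intervention year is not such a fact. A clinic with an active champion might call patients in more or less often, or patients might move between clinics. The two arms could then differ in who is counted as well as in how they are treated.

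The missing attribution rule makes this worse. An analyst who meets a patient with claims in both arms could count that patient twice, drop the patient, or choose an arm after the data are in. The plan rules out none of these, and they can give different primary results. The described models nest time periods within patients, so such a patient's practice is also undefined for any adjustment for clustering by practice.

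**Working it through.** **1. Timing.** Section 6.1 places selection of clinics for randomisation in months 1-3. Section 2 (description of the intervention) places training in months 4-9, with the project year after that. The intervention year in sections 3 and 4.1 therefore falls after randomisation. The précis window can be met entirely from earlier claims. The two windows define different cohorts: a patient first seen during the project year enters under section 4.1 but not under the précis.

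**2. Reproducing the stated power (section 9.2).** Inputs: 500 patients per group at Ochsner and 2,000 at USMM, 4 quarterly values each, a 20% reduction for correlation, a 0.10 SD effect and a 5% level. Sidedness is not stated; two-sided reproduces the figures.

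- Ochsner: 500 × 4 × 0.8 = 1,600 per group.
- USMM: 2,000 × 4 × 0.8 = 6,400 per group.
- Power = Φ(d / √(2/n) − 1.96), where d is the effect in SD units.
- Ochsner, d = 0.10: 0.10 / 0.03536 = 2.828, so power is 80.7% (stated 80%).
- USMM, d = 0.10: 99.99% (stated almost 100%). USMM, d = 0.05: 80.7% (stated 80%).

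Ochsner has little slack: 80% power needs 1,570 per group and 1,600 are planned. The 20% covers correlation only.

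**3. Illustration of overlap.** Let f be the share of each arm's patients who are also seen in the other arm. The documents do not give f, so the values below are assumptions. Three models are shown:

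- A: these patients contribute no contrast and the standard error is unchanged. The effect is 0.10(1−f).
- B: the same patients are counted in both arms and the analysis recognises this. The effect is 0.10(1−f) and the variance of the difference also falls by (1−f). This is the same as using n(1−f) at 0.10 SD.
- C: each patient has one arm and half of the contrast is lost. The effect is 0.10(1−f/2).

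| f (assumed) | Ochsner A | Ochsner B | Ochsner C | USMM at 0.10 SD, A |
|---|---|---|---|---|
| 5% | 76.6% | 78.7% | 78.7% | above 99.9% |
| 10% | 72.1% | 76.5% | 76.6% | 99.9% |
| 20% | 61.9% | 71.6% | 72.1% | 99.5% |

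Example, A at f = 10%: 0.09 / 0.03536 = 2.546, less 1.96 is 0.586, and Φ(0.586) = 72.1%. USMM power at 0.05 SD falls exactly as the Ochsner columns do. All rows take the plan's effective sample sizes as given.

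**The case against.** A reader might infer that the one-claim rule places a patient in both arms and so dilutes the effect. The documents do not support that. Section 4.1(a) decides who enters the study, and a participating practice can be in either arm. Arm is set separately, from the practice. Nesting time periods within patients suggests one series per patient, and nothing enters a patient twice. The section 9.5 wording on engagement is an intent-to-treat statement, not evidence of cross-arm counting. The defect is silence about patients with several practices, plus a window that contradicts other sections.

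A reader might also take the lower power figures as an established loss. They are not. Nothing in the documents shows whether overlap is 1% or 20%. Model A is the most pessimistic of the three because it removes the contrast but leaves the standard error unchanged. USMM, with 4,000 of the roughly 5,000 patients, is hardly affected at 0.10 SD. Much of any loss would come from patients really treated in both arms, which no attribution rule can undo.

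Finally, on the précis and section 9.1 reading, much of the selection argument falls away. That is true, but sections 3, 4.1 and 6.2.1 state the other window and the plan does not say which governs. The conflict and the missing rule both stand.

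**Conclusion.** The point holds as a contradiction over the eligibility window combined with a missing attribution rule. Neither depends on any assumed overlap. If section 4.1 is followed, cohort membership and arm can depend on post-randomisation visits; under either window, a patient with qualifying claims in both arms has no defined treatment value.

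The numerical effect cannot be found from the documents. The illustrative ranges show that Ochsner, and USMM at 0.05 SD, would be sensitive to moderate overlap, while USMM at 0.10 SD would not. They assume two-sided 5% testing, the plan's effective sample sizes and the stated values of f. This should be settled before outcome data are analysed, but it does not show that the trial is underpowered or that its result would be biased.

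**What to change.** - Use one eligibility window throughout: the pre-intervention one. Amend sections 3, 4.1 and 6.2.1 to match the précis and section 9.1.
- Attribute each patient to exactly one practice from claims in a fixed window ending before randomisation. One workable rule is the practice with the most primary care evaluation and management visits, with ties going to the most recent. Other fixed rules would also remove the ambiguity.
- Keep that practice and its arm for the whole analysis, whatever visits follow.
- Report by arm how many patients are later seen at a practice in the other arm, and add a sensitivity analysis without them. Treat that analysis as supportive, because it conditions on visits after randomisation.

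**Cost.** SAP wording and one attribution step on claims data already held. Patients first seen after the window closes are not counted. Six months of training separate randomisation from launch, so some patients will have changed clinic by then. They stay in the arm of their attributed practice, which adds some dilution.
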